8.4. Treatment Compliance

LJPC-501 will be administered to eligible patients by a qualified healthcare professional under the supervision of either the Investigator or Sub-Investigator(s).

The pharmacist will maintain records of LJPC-501 receipt, preparation, and dispensing, including the applicable lot numbers, and the patient's body weight.

8.5. Procedures

8.5.1. Screening

The following assessments will be performed during Screening:

- Obtain informed consent from patient's parent(s) or legal guardian(s). Assent will be obtained from the patient, if possible, per the institution's guidelines.
- Assess inclusion and exclusion criteria
- Obtain the patient's complete medical history, including the demographic information, diagnosis, surgical history, concurrent medical conditions, concomitant medications, and concomitant procedures
- Perform a limited physical examination, focusing on extremities, abdominal region, neurological system, body weight, and height.
- Titrate patient's SOC vasopressors to an age-, size-, and disease-appropriate MAP (Appendix A)
- Perform chest X-ray (optional)
- Assess vital signs: BP, respiratory rate (RR), and body temperature
- Assess HR and MAP hourly during Screening for a minimum of 2 hourly readings, within 24 hours prior to LJPC-501 treatment initiation. The average of 2 MAP readings (when total sum NED is > 0.1 μg/kg/min) will determine the Screening MAP.
- Perform 12-lead electrocardiogram (ECG), if possible
- Perform arterial blood gas (ABG) within 6 hours prior to LJPC-501 administration
- Collect blood samples for hematology and clinical chemistry within 6 hours prior to LJPC-501 administration
- Serum pregnancy test for females of childbearing potential
- Collect blood sample for angiotensin I and II, if possible

- Perform PELOD/PRISM/PIM2 assessments not completed in assessments above, within 6 hours prior to LJPC-501 administration (Section 10.4)
 - Pupillary reactions
 - Glasgow Coma Score
 - Diagnosis ratings for PIM2: high risk diagnosis score, low risk diagnosis score, elective admission, recovery post procedure, cardiac bypass
- Document urine output and fluid intake for the 24 hours prior to LJPC-501 administration, if available

8.5.2. Baseline

- Titrate patient's SOC vasopressors
- Assess vital signs: BP, RR, and body temperature
- Assess HR and MAP at approximately -15 min, -5 min and 0 min (or just prior to initiation of LJPC-501). The average of the 3 MAP values will determine the Baseline MAP.
- Monitor urine output and fluid intake
- Collect blood sample for serum lactate (arterial or venous)
- Record tissue oxygen saturation
- Record concomitant medications and procedures

8.5.3. Day 1 (0 to 2 hours)

- Administer LJPC-501
- Assess vital signs: HR, MAP, BP, RR, and body temperature
 - HR and MAP should be measured once every 5 minutes during the first
 15 minutes of treatment, then once every 15 minutes up to the Hour 2 timepoint
 - At Hour 2, record HR and MAP without changing doses of LJPC-501 or other vasopressors (for assessment of primary endpoint)
- At Hour 2, collect blood sample for serum lactate (arterial or venous)
- At Hour 2, record tissue oxygen saturation
- Monitor urine output and fluid intake hourly
- Record concomitant medications and procedures
- Assess AEs and SAEs

8.5.4. Day 1 (2 to < 24 hours)

• Administer LJPC-501

- Assess vital signs: HR, MAP
 - HR and MAP should be measured at least once hourly and prior to any dose adjustment through the duration of LJPC-501 administration.
- Monitor urine output and fluid intake hourly
- Titrate SOC vasopressors, with the goal of reducing reliance on catecholamines
- Record concomitant medications and procedures
- Assess AEs and SAEs

8.5.5. Hour 24 (± 1 hour)

- Continue to administer LJPC-501 at Investigator's discretion. If continuing, notify Sponsor. If not continuing, complete all Hour 24 procedures before beginning to down-titrate LJPC-501 dose to stop administration (see Section 8.3.2 for down-titration guidance).
- Assess LJPC-501 dose.
- Assess MAP without changing doses of LJPC-501 or other vasopressors (for assessment of secondary endpoint)
- Assess HR
- Collect blood sample for serum lactate (arterial or venous)
- Record tissue oxygen saturation
- Assess other vital signs: BP, RR, and body temperature
- Perform 12-lead ECG, if possible
- Perform ABG
- Collect blood samples for hematology and clinical chemistry:
- Perform PELOD/PRISM/PIM2 assessments completed in assessments above (Section 10.4)
 - Pupillary reactions
 - Glasgow Coma Score
 - Diagnosis ratings for PIM2: high risk diagnosis score, low risk diagnosis score, elective admission, recovery post procedure, cardiac bypass
- Monitor urine output and fluid intake
- Assess AEs and SAEs
- Record concomitant medications and procedures

8.5.6. Day 2 to 6, if LJPC-501 Administered after Hour 24

- Continue to administer LJPC-501 at Investigator's discretion. To discontinue at any time after Hour 24, down-titrate LJPC-501 dose to stop administration after procedures for that day are completed (see Section 8.3.2 for down-titration guidance)
- Titrate SOC vasopressors, with the goal of reducing reliance on catecholamines
- Assess HR and MAP prior to any dose adjustment and a minimum of hourly through discontinuation of LJPC-501
- Assess BP, RR, and body temperature once daily
- Monitor urine output and fluid intake hourly
- Record concomitant medications and procedures
- Assess AEs and SAEs

8.5.7. Day 2 to 6, if LJPC-501 NOT Administered after Hour 24

- Assess vital signs: HR, MAP, BP, RR, and body temperature once daily
- Monitor urine output and fluid intake per local practice
- Record concomitant medications and procedures
- Assess AEs and SAEs

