5.5. Exploratory Endpoints

- Change in tissue oxygenation from baseline to 2 hours and to 24 hours
- Change in HR from baseline to 2 hours
- Change in sum NED from baseline to 24 hours
- 28-day all-cause mortality
- Number of ventilator days
- Number of days on a vasopressor
- Change in PRISM and PIM2 scores from Screening to 24 hours

La Jolla Pharmaceutical Company - Confidential 19 March 2018 (Version 2.0)

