- ¹⁷ Blood for clinical chemistry and hematology testing will be collected at Screening (within 6 hours prior to LJPC-501 administration), and at Hour 24 (Section 11.1.8).
- ¹⁸ If total blood collection volume limits (per institutional guidelines) allow, blood samples will be collected for angiotensin I/II levels.
- ¹⁹ See Section 6.2 and Section 6.6 for study periods and dose adjustment guidelines. (X) indicates time periods during which dose administration is optional.
- ²⁰ All parameters of the PELOD/PRISM/PIM2 scores should be performed at Screening and at Hour 24. The Screening PELOD/PRISM/PIM2 scores must be determined with data obtained no more than 6 hours prior to initiation of LJPC-501 dosing. See Appendix C, Appendix D, and Appendix E.
- ²¹ Record all concomitant medications (including vasopressors) and any procedures performed through Day 28. In addition, record all vasopressors administered up to 2 days prior to beginning LJPC-501 administration. Total daily dose for each vasopressor administered through Day 28 may be recorded after completion of LJPC-501 administration.
- ²² Safety will be evaluated at every time point. On Day 28, a phone call follow-up to the patient's parent(s) or legal guardian(s), the patient's primary care physician, and/or a chart review will be conducted to determine if reportable safety events occurred between EOS and Day 28.

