10.4. PELOD/PRISM/PIM2 Scoring

Risk scoring indices will include the PELOD, PRISM, and PIM2 scores (Table 6).

All components of the PELOD, PRISM, and PIM2 scores will be collected during Screening, employing data obtained no more than 6 hours prior to initiation of LJPC-501 dosing. In addition, all components of PELOD, PRISM, and PIM2 scores will be collected at Hour 24 after the initiation of LJPC-501. The PELOD score is the sum of the 6 individual item scores (Appendix C). The PRISM score is the sum of the 14 individual item scores (Appendix D). The PIM2 score is the sum of the 10 individual item scores (Appendix E).

PELOD	PRISM	PIM2	
	Common to All		
Systolic BP	Systolic BP	Systolic BP	
Pupillary reactions	Pupillary reactions	Pupillary reactions	
PaO ₂ /FiO ₂	PaO ₂ /FiO ₂	$FiO_2 \times 100/PaO_2$	
	Common to 2 Scores		
Heart rate	Heart rate		
PTT or INR	PT/PTT		
Glasgow score	Glasgow score		
PaCO ₂	PaCO ₂		
Mechanical ventilation		Mechanical ventilation during first hour in ICU	
	Unique		
AST/SGOT	Bicarbonate (mEq/L)	Base excess (mmol/L) in arterial or capillary blood	
Creatinine	Total bilirubin	High risk diagnosis score	
Platelets	Calcium	Low risk diagnosis score	
WBC	Potassium	Elective admission	
	Glucose	Recovery post procedure	
	Diastolic BP	Cardiac bypass	
	Respiratory rate		

Table 6: Assessments Included in Each Pediatric Mortality Risk Score

Abbreviations: AST=aspartate transaminase; BP=blood pressure; FiO₂=fractional inspired oxygen; ICU=intensive care unit; INR=international normalized ratio; mEq=milliequivalent; PaO₂=arterial oxygen partial pressure; PaCO₂=carbon dioxide partial pressure; PELOD=Pediatric Logistic Organ Dysfunction; PIM2=Pediatric Index of Mortality 2; PRISM=Pediatric Risk of Mortality; PT=prothrombin time; PTT=partial thromboplastin time; SGOT= serum glutamic-oxaloacetic transaminase; WBC=white blood cells.

Assessments for PELOD, PRISM, and PIM2 scores are drawn from multiple sources, and Investigators should ensure all assessments are performed within the time windows for Screening (within 6 hours prior to LJPC-501 administration) and Hour 24 (± 1 hour).

- Vital signs: systolic BP, diastolic BP, HR, RR
- Hematology and serum chemistry: PTT, INR, AST, creatinine, platelets, WBC, total bilirubin, calcium, potassium, glucose
- ABG: PaO₂/FiO₂, PaCO₂, bicarbonate, base excess

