- Physician assessed: pupillary reactions, Glasgow Coma Score (Appendix F), mechanical ventilation, diagnosis ratings for PIM2 (high risk diagnosis score, low risk diagnosis score, elective admission, recovery post procedure, cardiac bypass [Appendix E]).

Scores should be calculated with the most recent values prior to the assessment time point. Missing values will be assigned the last observation carried forward if missing for reason other than death or treatment failure. Missing values at Hour 24, due to death or treatment failure, will be assigned the worst possible score.

The Glasgow Coma Score (Appendix F) should be completed during a sedation holiday, if possible. If not, then the most recent non-sedated value should be used.

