APPENDIX E. PIM2 SCORING

Source: Slater 2003

Abbreviations: PaO₂=arterial oxygen partial pressure; FiO₂=fractional inspired oxygen.

Use the most recent values for the calculation of PIM2. If information is missing (eg, base excess is not measured) record 0, except for systolic blood pressure, which should be recorded as 120.

^a High risk diagnoses. If in doubt record 0.

Cardiac arrest preceding intensive care unit (ICU) admission

Severe combined immune deficiency

Leukemia or lymphoma after first induction

Spontaneous cerebral hemorrhage

Cardiomyopathy or myocarditis

- Hypoplastic left heart syndrome
- HIV infection

Liver failure is the main reason for ICU admission

Neurodegenerative disorder

^b Low risk diagnoses. If in doubt record 0.

Asthma is the main reason for ICU admission

Bronchiolitis is the main reason for ICU admission

Croup is the main reason for ICU admission

Obstructive sleep apnea is the main reason for ICU admission

Diabetic ketoacidosis is the main reason for ICU admission

Calculation:

Logit = $(-4.8841) + (values \times Beta) + (0.01395 \times (absolute(SBP-120))) + (0.1040 \times (absolute base excess)) + (0.2888 \times (100 \times FiO_2/PaO_2))$

PIM2 Score = Predicted death rate = eLogit/ (1+eLogit)

APPENDIX F.	GLASGOW COMA SCORE
--------------------	---------------------------

Spontaneous – open with blinking at baseline	4
Opens to verbal command, speech, or shout	3
Opens to pain, not applied to face	2
None	1
Oriented	5
Confused conversation, but able to answer questions	4
Inappropriate responses, words discernible	3
Incomprehensible speech	2
None	1
Obeys commands for movement	6
Purposeful movement to painful stimulus	5
Withdraws from pain	4
Abnormal (spastic) flexion, decorticate posture	3
Extensor (rigid) response, decerebrate posture	2
None	1
	Opens to verbal command, speech, or shout Opens to pain, not applied to face None Oriented Confused conversation, but able to answer questions Inappropriate responses, words discernible Incomprehensible speech None Obeys commands for movement Purposeful movement to painful stimulus Withdraws from pain Abnormal (spastic) flexion, decorticate posture Extensor (rigid) response, decerebrate posture

The Glasgow Coma Score should be completed during a sedation holiday, if possible. If not, then the most recent non-sedated value should be used.

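### The PIM2 admission and diagnosis items are rated again at Hour 24, so an operation after Screening can lower the exploratory PIM2 score with no change in physiology

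*Protocol*

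**What the plan says.** Section 8.5.5 (Hour 24) lists among the site's tasks: "Diagnosis ratings for PIM2: high risk diagnosis score, low risk diagnosis score, elective admission, recovery post procedure, cardiac bypass". Section 8.5.1 has the same list at Screening.

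Two other places confirm that the repeat is intended. Section 10.4 states: "In addition, all components of PELOD, PRISM, and PIM2 scores will be collected at Hour 24 after the initiation of LJPC-501". Table 4 footnote 20 states: "All parameters of the PELOD/PRISM/PIM2 scores should be performed at Screening and at Hour 24".

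On which value to use, Section 10.4 says "Scores should be calculated with the most recent values prior to the assessment time point" and Appendix E says "Use the most recent values for the calculation of PIM2". Neither exempts the admission and diagnosis items, and no provision carries the Screening rating of these items forward as a matter of course.

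Appendix E gives recovery post procedure (Yes = 1) a coefficient of -1.0244 and cardiac bypass (Yes = 1) a coefficient of 0.7507. It converts the logit to a predicted death rate. Its footnotes define only the high-risk and low-risk diagnoses. Some of those entries are worded by the admission, for example "Liver failure is the main reason for ICU admission".

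Section 5.5 lists the endpoint concerned: "Change in PRISM and PIM2 scores from Screening to 24 hours". Section 6.1 describes it as an exploratory measure of mortality risk.

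**The concern.** A change score should move because the patient's condition moved. Elective admission, by its name, describes how the child came to be admitted, and the low-risk diagnosis entries are each worded as the main reason for ICU admission. A drug started later cannot alter such facts. Recovery post procedure and cardiac bypass are more troublesome, because the protocol neither defines them nor says which point in time they refer to. Combined with a second rating and a latest-value rule, this lets a rater who reads the text literally mark Yes at Hour 24 for a child who had an operation after the Screening rating.

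The coefficient for recovery post procedure is negative, so that child's predicted death rate falls even if pupils, blood pressure, base excess, oxygenation and ventilation are all unchanged. The trial has one arm and 10 to 30 patients, so there is no control group in which the same artefact would appear and cancel. At stake is the interpretation of one descriptive exploratory result.

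**Working it through.** **Inputs.** All coefficients are from Appendix E: intercept -4.8841; recovery post procedure -1.0244; cardiac bypass +0.7507; mechanical ventilation +1.3352; 0.01395 per mmHg of |SBP - 120|; 0.1040 per mmol/L of absolute base excess; 0.2888 per unit of 100 × FiO2/PaO2. The protocol gives no patient values and no PIM2 result, so there is no stated figure to reproduce, and the starting rates below are assumptions.

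**Interval between ratings.** Screening components may date from up to 6 hours before dosing, and the Hour 24 window is ± 1 hour. The two ratings can therefore be up to 6 + 24 + 1 = 31 hours apart.

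**Shift in one child.** With everything else fixed, p' = 1/(1 + exp(-(logit(p) + shift))).

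- Recovery post procedure newly Yes: shift = -1.0244, odds ratio exp(-1.0244) = 0.359.
- Cardiac bypass also newly Yes: shift = -1.0244 + 0.7507 = -0.2737, odds ratio exp(-0.2737) = 0.761.

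| Assumed rate at Screening | Recovery newly Yes | Recovery and bypass newly Yes |
|---|---|---|
| 5% | 1.9% | 3.9% |
| 10% | 3.8% | 7.8% |
| 20% | 8.2% | 16.0% |
| 30% | 13.3% | 24.6% |
| 50% | 26.4% | 43.2% |

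**One worked child (assumed values).** Ventilated, SBP 85 mmHg, base excess -8 mmol/L, FiO2 0.6, PaO2 80 mmHg, all other items No:

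logit = -4.8841 + 1.3352 + 0.01395 × 35 + 0.1040 × 8 + 0.2888 × (100 × 0.6/80) = -2.012, a predicted rate of 11.8%.

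With recovery post procedure switched to Yes the logit is -3.036 and the rate 4.6%. With bypass switched as well, the rate is 9.2%.

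**Scale of the coefficient.** 1.0244/0.1040 = 9.85, so the switch counts as much as an improvement of about 9.9 mmol/L in absolute base excess.

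**Effect on the reported mean.** One child going from 20% to 8.2% contributes 11.8 percentage points. The mean change moves by 11.8/10 = 1.2 points with 10 patients and 11.8/30 = 0.4 with 30.

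**After the fix.** With the five items held at Screening, an intervening operation with unchanged physiology shifts the logit by 0.

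**Form of the score.** Section 10.4 calls PIM2 a sum of ten item scores, whereas Appendix E uses an intercept and an inverse logit. The Appendix E form is used here. The recovery item lowers the score under either description.

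**The case against.** Several objections have force.

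- *The item is not anchored to admission in the document.* Appendix E's footnotes attach only to the high-risk and low-risk diagnoses. A reader might infer that the protocol itself defines recovery post procedure as an admission fact, so that a Yes at Hour 24 is an error. It does not say so. What stands is narrower: the item is required twice and is left without a time reference.
- *Not every re-rating is noise.* A reader might infer that any difference between the two diagnosis ratings is a rater difference. The text does not support that. Most high-risk entries, such as spontaneous cerebral hemorrhage or myocarditis, carry no admission wording, and one newly found between ratings would be real clinical information. Appendix E also tells raters to record 0 when in doubt.
- *The effect is conditional.* It needs an operation between ratings, a No at Screening and a rater who reads the item literally. A rater who ties it to admission records no change.
- *The direction is not fixed in practice.* A newly Yes bypass rating offsets most of the shift, and new ventilation would reverse it (-1.0244 + 1.3352 = +0.3108). The latter, however, is no longer a case of unchanged patient status.
- *It can be repaired in analysis.* Components are collected at both times and procedures are recorded through Day 28, so an SAP (not seen here) could hold the items constant. That rule would, however, conflict with what Section 10.4 and Appendix E now instruct.

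**Conclusion.** The point holds as a minor one. The protocol tells sites to rate all five items again and to score on the latest values. Because recovery post procedure and cardiac bypass lack a time reference, an operation between Screening and Hour 24 can lower a child's PIM2 score for reasons unrelated to physiology or to LJPC-501. For an affected child the odds of death are multiplied by 0.359, or by 0.761 if bypass is also newly Yes. For the cohort, one child starting from an assumed 20% moves the mean change by about 1.2 percentage points at n = 10 and 0.4 at n = 30.

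The size rests on assumed starting rates, and the number of children affected is not stated, so no overall bias can be given. It would go too far to infer that the trial's efficacy conclusion is at risk. Success depends on the Hour 2 MAP/NED composite, and the secondary organ-dysfunction score, PELOD, contains none of these five items. Only the exploratory PIM2 change is touched.

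**What to change.** For the Screening-to-Hour 24 change in PIM2, hold high-risk diagnosis, low-risk diagnosis, elective admission, recovery post procedure and cardiac bypass at their Screening ratings. To do this:

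1. Delete the PIM2 diagnosis-ratings bullet from Section 8.5.5.
2. In Section 10.4 and Table 4 footnote 20, exempt these five items from the requirement to collect every component again at Hour 24.
3. In Section 10.4 and Appendix E, state that the latest-value rule does not apply to these five items.
4. Write a separate, explicit Hour 24 rule for the mechanical ventilation item. Table 6 ties it to the first hour in ICU, while Appendix E lists it without a time, so a rule covering only the five items would leave it unsettled.

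The cost is wording only, and sites have one task fewer at Hour 24. A diagnosis newly made after Screening would no longer enter the PIM2 change; it can be described separately.

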8.5.8. Day 7, if LJPC-501 Administered

- Continue to administer LJPC-501 at Investigator's discretion
- Assess HR and MAP prior to any dose adjustment and a minimum of hourly through discontinuation of LJPC-501
- Assess BP, RR, and body temperature once daily
- Monitor urine output and fluid intake hourly
- Record concomitant medications and procedures
- Assess AEs and SAEs
- Discontinue LJPC-501 administration by down titration after procedures are completed (see Section 8.3.2 for down-titration guidance)

8.5.9. Day 7, if LJPC-501 NOT Administered

- Monitor urine output and fluid intake per local practice
- Perform EOS procedures

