A schedule of study procedures is shown in Table 4. Patients will be monitored for hemodynamic vital signs (MAP, HR) at Screening and at approximately -15, -5 and 0 minutes (or just prior to initiation of LJPC-501 dosing) to establish the Baseline MAP value. MAP should be assessed once every 5 minutes during the first 15 minutes of LJPC-501 treatment, then once every 15 minutes up to the Hour 2 time point and at least once hourly thereafter through the duration of LJPC-501 administration (at minimum 24 hours). Additionally, MAP should be assessed just prior to every dose titration. If LJPC-501 administration is continued for longer than 24 hours, MAP should be assessed hourly and just prior to any dose adjustment until LJPC-501 is discontinued.

[figure not shown]
Treatment with LJPC-501 will continue to Hour 24, with the goal of maintaining age-, size-, and disease-appropriate MAP (Appendix A, Dellinger 2013), while reducing the reliance on SOC vasopressors. Down-titration of SOC vasopressors should be done according to individual institutional protocols and the Investigator's discretion.

After 24 hours, LJPC-501 treatment may be stopped or continued up to 7 days (168 hours) at the Investigator's discretion. It is recommended that the Investigator check in with the Sponsor's contact to continue treatment for more than 24 hours. If the Investigator determines that it is necessary to discontinue LJPC-501 prior to Hour 24, the Sponsor should also be consulted prior to discontinuation. To stop treatment, LJPC-501 will be titrated off by decreasing the dose at the Investigator's discretion and according to guidelines in Section 8.3.2. After Hour 24, if LJPC-501 treatment has been stopped for 3 hours or less, the Investigator may reinitiate treatment after consultation with Sponsor; if treatment has been stopped for more than 3 hours it may not be reinitiated. All patients will be followed for a minimum of 7 days, or for 72 hours (3 days) \pm 6 hours following discontinuation of LJPC-501, whichever is later, before end-of-study (EOS) assessments.

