² Patients will be followed for a minimum of 7 days, or for 72 hours (3 days) ± 6 hours following discontinuation of LJPC-501, whichever is later, before end of study (EOS) assessments are completed. Depending on the duration of treatment, EOS may occur on Day 7 through Day 10. If a patient is treated for the target minimum of 24 hours, EOS will occur on Day 7.

³ Informed consent must be obtained before any study related activities can occur. SOC procedures conducted prior to informed consent may be used to qualify patients for the study, if performed within the specified time window for the procedure (Section 8.5).

⁴ All patients will have their SOC vasopressors titrated (to a total sum NE equivalent dose of > 0.1 μg/kg/min to be eligible) for a minimum of 2 hours but not for longer than 48 hours prior to initiation of LJPC-501 dosing. During the first two hours of LJPC-501 treatment, SOC vasopressor dosing may be decreased, but not increased, unless adjustment is required for safety reasons. After Hour 2 and throughout LJPC-501 treatment, up to Day 7, titration of SOC vasopressors may continue with the goal of sparing the use of catecholamines. (X) indicates time periods during which LJPC-501 dose administration is optional. During treatment with LJPC-501, SOC vasopressor titration should be tracked.

⁵ Do not continue administration for more than 7 days (168 hours).

⁶ A limited physical exam (PE) focused on extremities, abdominal region and neurological system should be performed at Screening and at EOS. Screening PE will also document body weight and height.

⁷ Chest X-ray is optional. SOC chest X-rays collected prior to informed consent but within 24 hours prior to LJPC-501 treatment initiation may be used.

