8.5.10. EOS (Day 7 to 10, variable)

• Perform a limited physical examination, focusing on extremities, abdominal region, and neurological system

- Assess vital signs: HR, MAP, BP, RR, and body temperature
- Record concomitant medications and procedures
- Assess AEs and SAEs

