11.2.4. Reporting of Adverse Events and Serious Adverse Events

11.2.4.1. Reporting of Adverse Events

All AEs will be recorded from initiation of study drug treatment, during treatment, and through EOS, regardless of the causal relationship to the investigational product.

All AEs, whether believed by the Investigator to be related or unrelated to the investigational product, must be documented in the patient's medical records/source documents, in accordance with the Investigator's normal clinical practice and on the AE CRF. Each AE is to be evaluated for duration, intensity, frequency, seriousness, outcome, other actions taken, and relationship to the investigational product.

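### Section 8.5.9 orders EOS on Day 7 for every patient off LJPC-501, which contradicts the protocol's own 72-hour post-discontinuation rule for patients stopped on Day 5 or 6

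*Protocol*

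**What the plan says.** The visit list in Section 8.5 has two Day 7 blocks. Section 8.5.8 covers patients still being dosed. Section 8.5.9 is headed "Day 7, if LJPC-501 NOT Administered", and after urine output and fluid monitoring its only instruction is "Perform EOS procedures". It does not mention the time of the last dose.

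The timing rule is given elsewhere. Section 6.2 states that "All patients will be followed for a minimum of 7 days", with an alternative period counted from the end of dosing. Table 4 footnote 2 (printed under Section 6.7) words that alternative as "for 72 hours (3 days) ± 6 hours following discontinuation of LJPC-501, whichever is later". The synopsis gives the same rule. The footnote adds: "Depending on the duration of treatment, EOS may occur on Day 7 through Day 10". It ties a Day 7 EOS to the patient treated for the 24-hour target. The heading of Section 8.5.10 also describes EOS as variable, from Day 7 to Day 10.

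Section 8.5.6 allows LJPC-501 to be discontinued at any time after Hour 24, so stops on Day 5 or 6 can occur.

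On safety collection, Section 11.2.4.1 says: "All AEs will be recorded from initiation of study drug treatment, during treatment, and through EOS". Section 11.2.4.2 takes serious adverse events (SAEs) through Day 28. Table 4 footnote 21 does the same for concomitant medications and procedures. Under Section 11.1.2 the limited physical examination is done only at Screening and EOS.

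**The concern.** A patient stopped on Day 5 or 6 is off drug on Day 7 and so falls under the heading of Section 8.5.9. That section closes the patient out on Day 7. Section 6.2 and Table 4 footnote 2 close the same patient out later, on Day 8 or Day 9 for most such stops.

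Because recording of all adverse events (AEs) ends at EOS, the choice of section sets the length of the AE window. It also sets the timing of the only post-dose examination of extremities, abdomen and neurological system. The patients concerned have had more than about four days of exposure. Sites that follow 8.5.9 and sites that follow 6.2 would observe them for different lengths of time. Safety is a secondary endpoint here, reported descriptively in 10 to 30 patients, so a difference between sites in the observation window is hard to see or correct afterwards.

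**Working it through.** **Inputs.** Minimum follow-up is 7 days = 168 h (Section 6.2). The post-drug requirement is 72 h, or 66 h at the lower edge of the ± 6 h window (Table 4 footnote 2). Maximum treatment is 168 h (Table 4 footnote 5). Assumption: Day n runs from Hour 24(n − 1) to Hour 24n, so Day 5 is Hours 96–120, Day 6 is Hours 120–144 and Day 7 is Hours 144–168.

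**Reproducing the stated EOS range.** For a stop at hour s, the rule gives EOS = max(168, s + 72).
- s = 24: max(168, 96) = 168 h, the end of Day 7.
- s = 168: max(168, 240) = 240 h, the end of Day 10.

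This matches the stated Day 7 to Day 10, including the Day 7 EOS for 24 hours of treatment.

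**Literal reading of 8.5.9.** Take EOS at Hour 168, the earliest nominal time that respects the 7-day minimum. Post-drug follow-up is 168 − s, and the shortfall is max(0, 72 − (168 − s)).

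| Stop hour s | EOS under the rule | Follow-up if EOS at 168 h | Shortfall against 72 h | Shortfall against 66 h |
|---|---|---|---|---|
| 96 | 168 | 72 | 0 | 0 |
| 102 | 174 | 66 | 6 | 0 |
| 108 | 180 | 60 | 12 | 6 |
| 120 | 192 | 48 | 24 | 18 |
| 132 | 204 | 36 | 36 | 30 |
| 144 | 216 | 24 | 48 | 42 |

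A Day 5 stop loses 0–24 h (0–33% of 72 h), and stops up to Hour 102 still meet the 66 h edge. A Day 6 stop loses 24–48 h (33–67%). Stops at or before Hour 96 lose nothing. Patients still on drug on Day 7 come under 8.5.8 and are not affected.

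**Sensitivity to the EOS hour.** If EOS is held at Hour 174, using the upper end of the ± 6 h in the Table 4 EOS column, the losses are 0–18 h (Day 5) and 18–42 h (Day 6). If it is held at mid-Day 7 (Hour 156), they are 12–36 h and 36–60 h, but that also breaks the 7-day minimum.

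**What does not move.** Day 28 is Hour 672. A stop at Hour 96 leaves 576 h (24 days) of SAE collection, and a stop at Hour 144 leaves 528 h (22 days), whichever section sets EOS.

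**The case against.** The strongest reply is that the rule is not in doubt. It stands in the synopsis, Section 6.2 and Table 4 footnote 2, and the section right after 8.5.9 is headed with a variable EOS. Section 8.5.9 could also be read as the Day 7 continuation of Section 8.5.7, which covers patients not dosed after Hour 24. For them a Day 7 EOS is correct.

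The first part stands and keeps the severity low, since a careful site has the governing rule to hand. The second part does not remove the problem. The 8.5.9 heading drops the Hour 24 qualifier that 8.5.7 carries. If the qualifier is read back in, patients stopped on Day 5 or 6 have no Day 7 block at all, because 8.5.8 covers only those on drug.

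Three stronger readings are tempting and are not supported:

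- A reader might infer that these patients lose most of their post-drug safety follow-up. They do not. SAEs, concomitant medications and procedures run through Day 28, and Section 11.2.5 requires continued follow-up of related or clinically significant AEs that are ongoing at the final visit. Even within the 72-hour window, with EOS at Hour 168, more than half is lost only for stops after Hour 132.
- A reader might infer that sites have no route to a later EOS. Section 8.5.10 allows one through Day 10, and Table 4 footnote 8 requires daily MAP and HR after treatment until EOS, with no cut-off at Day 6.
- A reader might compute a loss of about 71 h, from a stop at Hour 143 and EOS at Hour 144. That places EOS a day short of the separate 7-day minimum. With EOS at Hour 168 the same stop loses 72 − 25 = 47 h.

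The Table 4 safety row is labelled for both AEs and SAEs and is marked at Day 28, which might suggest that non-serious events are picked up later. But Section 8.5.11 names only SAEs at that contact, and Section 11.2.4.1 ends all-AE recording at EOS.

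**Conclusion.** The contradiction is real, and the passages must be reconciled. It affects patients who stay in the study, stop LJPC-501 after about Hour 96 and are off drug before Day 7. With EOS at Hour 168, a literal 8.5.9 removes 0–24 h of the required 72 h for a Day 5 stop and 24–48 h for a Day 6 stop. The loss is recording of new non-serious AEs in that interval; the EOS vital signs and limited examination still take place, but too early.

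The figures rest on the 24-hour day convention above and on EOS respecting the 7-day minimum. The protocol gives no basis for estimating how many of the 10 to 30 patients would stop on Day 5 or 6, or how many sites would follow 8.5.9 over Section 6.2. Severity is low: this is one unqualified line in a visit list, set against a rule stated correctly in three other places.

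**What to change.** Make the Section 8.5.9 instruction conditional on the protocol's existing rule. Possible wording: *Perform EOS procedures if the follow-up required by Section 6.2 and Table 4 footnote 2 (72 h ± 6 h since discontinuation) is complete; otherwise continue daily assessments and AE recording until EOS.*

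Also state in Section 8.5.7 that the off-drug daily assessments continue until EOS, and that they apply to patients stopped after Hour 24 as well.

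The cost is protocol wording. AE recording through EOS and daily MAP and HR until EOS are already required. Extending 8.5.7 in full would add daily BP, respiratory rate, temperature, and urine and fluid monitoring on Days 8 and 9 for the few patients concerned. The sponsor can limit the extension to what is already required if that is not wanted. Dosing is not touched.
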